6.4.2 Analysis of Primary Outcome of Interest

For Aim 1, PARDSEVERE biomarker levels will be used to classify subjects according to the previously published PARDSEVERE decision rules without modifications [45]. This allows for assignment of 28-day mortality risk based on allocation of study subjects to one of 5 terminal nodes. Performance of PARDSEVERE will be assessed by AUROC for discriminating 28-day mortality and other diagnostic accuracy measures, including sensitivity, specificity, and positive and negative predictive values at different probability cutoffs. PARDSEVERE will

be considered validated if sensitivity is ≥ 0.85 and specificity is ≥ 0.65 , both with 95% CI width ≤ 0.16 .

For Aim 2, we will perform mRNA gene expression, and identify endotypes using a previously published 100-gene classifier [42, 43].

For Aim 3, we will identify *de novo* endotypes using LCA including biomarker and clinical variables, or novel endotypes using the entire gene expression pattern.

For the transcriptomic part of Aims 2 and 3, the cohort will be split 60:40 into a derivation and test set. In Aim 2, we will determine genome-wide differential gene expression. After filtering and normalizing, gene expression values will be ranked by median absolute deviation across all patient samples. We will then perform unsupervised agglomerative hierarchical clustering on the top 5000 probesets, with clusters allowed $k = 2-12$, as has been done to discover mRNA-based endotypes in adult sepsis [50]. To estimate k (number of endotypes), we will combine cumulative distribution functions and cophenetic distance correlation analysis to assess clustering stability. Using a random forest classifier (supervised classification with high dimensional data methods)[50, 51], we will assess ARDS endotype classification with ten-fold cross-validation of stepwise increments in gene numbers. We will decide on the final number of endotype-defining genes when the process yields a cross-validation misclassification error rate of $< 10\%$.

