For the protein biomarker part of Aim 3, the cohort will be split 60:40 into a derivation and test set. We will use all measured plasma biomarkers and select clinical variables recorded within 24 hours of ARDS onset, including age, vasopressor-inotrope score [52], specific laboratory values including PELOD 2, bicarbonate, and OI at ARDS onset. These variables were chosen based on their ability to discriminate mortality in previous studies of adult [37] or pediatric ARDS [35], including by our group [34], and their ready availability within the first 24 hours of ARDS. All analyses will be performed blinded to outcome. As scales of variables vary considerably, continuous variables will be standardized to mean = 0 and standard deviation = 1 prior to analysis. We will consider models between 2 and 5 subclasses, as has been done for adult ARDS [37-39]. For LCA, criteria for model selection will be based on the Bayesian Information Criteria, the Vuong-Lo-Mendell-Rubin likelihood ratio test, and size of the smallest class. Model estimation will be based on full-information maximum likelihood methods. To avoid local maximum likelihood solutions, we will use 100 random starting values, of which the best 20 will be optimized.

For secondary aims, assuming a mortality rate of 16%, a 50:50 split between endotypes, and $\alpha = 0.05$, with 475 subjects we have 80% power to detect an association with an odds ratio ≥ 2.0 between endotype and 28-day mortality. Importantly, as the goal of endotype discovery is not mortality prediction [53], we are not powering for this outcome. Rather, we provide this calculation here for reference of what effect size endotype has on mortality that we will be able to observe.

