6.5 Sample Size and Power

For Aim 1, assuming a mortality rate of 16% and a PARDSEVERE sensitivity of 0.85 and specificity of 0.65, the sample size needed for two-sided 95% CI width of ≤ 0.16 (i.e., sensitivity of 0.85 with 95% CI 0.77 to 0.93) is 454 subjects. In our single-center study of 152 subjects and 16% mortality [45], our sensitivity was 0.96 and specificity was 0.66, suggesting that these assumptions are realistic. We have increased this to 500 total subjects with samples collected to account for ~10% of subjects being unevaluable due to sample loss or degradation during transport and storage.

For the transcriptomic Aims 2 and 3, we anticipate 475 evaluable subjects with sufficient RNA from the total cohort of 500 subjects with samples collected, assuming a conservative estimate of 5% drop-out due to neutropenia. As we found evidence for ARDS endotypes in our preliminary cohort of 67 subjects, we anticipate adequate numbers for endotype discovery. As a comparison, in adult sepsis, 4 endotypes were discovered using whole blood gene expression from 306 subjects [50].

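### The gene-number stopping rule (cross-validated error below 10%) can be met while an endotype holding under 10% of the derivation set is largely or wholly misclassified

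*Combined protocol and SAP*

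**What the plan says.** All of this is in the combined protocol and SAP. Section 6.4.2 states: "For the transcriptomic part of Aims 2 and 3, the cohort will be split 60:40 into a derivation and test set". On the clustering it says: "We will then perform unsupervised agglomerative hierarchical clustering on the top 5000 probesets, with clusters allowed" to number from 2 to 12. The number of endotypes, k, is estimated from stability measures: "we will combine cumulative distribution functions and cophenetic distance correlation analysis to assess clustering stability". A random forest is then trained on the resulting labels: "we will assess ARDS endotype classification with ten-fold cross-validation of stepwise increments in gene numbers". The stopping rule follows: "We will decide on the final number of endotype-defining genes when the process yields a cross-validation misclassification error rate of" less than 10%.

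The error rate carries no qualifier. For the transcriptomic part, sections 6.3 to 6.5 give no per-endotype sensitivity, balanced error, class weighting or minimum cluster size. They also give no per-endotype acceptance criterion for the 40% test set.

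The protein-biomarker part of Aim 3, in the same section, is handled differently. There the plan says "We will consider models between 2 and 5 subclasses" and lists how large the smallest class is among the criteria for choosing the latent class model.

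Section 6.5 supplies the denominator: "we anticipate 475 evaluable subjects with sufficient RNA from the total cohort of 500 subjects with samples collected".

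**The concern.** A single misclassification rate weights each endotype by its size. A small endotype contributes few errors even when every one of its patients is misplaced, so the rule can stop adding genes once the large endotypes are separated. It cannot tell a gene set that identifies every endotype from one that identifies only the large ones.

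This matters because identifying endotypes is the purpose of Aims 2 and 3, and section 2.2 then relates endotypes to mortality, ventilation duration and treatment response. Test-set patients have to be assigned to an endotype somehow. If the reduced gene set does this, a small endotype would be absorbed into larger ones there.

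**Working it through.** **Inputs.** 500 subjects with samples and 5% RNA drop-out (section 6.5); a 60:40 split, k from 2 to 12, and an error limit of 10% (section 6.4.2).

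**1. The plan's own figure.** 500 × (1 − 0.05) = 475, which reproduces the stated number. Derivation set: 0.60 × 475 = 285. Test set: 190.

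**2. What the limit allows.** 28/285 = 9.82% passes; 29/285 = 10.18% fails. An endotype of up to 28 patients can be missed entirely, but only if no other errors take the total above 28.

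**3. Room for other errors when a small endotype is wholly missed.**

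| Size of missed endotype | Share of 285 | Further errors allowed | Error rate allowed in the rest |
|---|---|---|---|
| 14 | 4.9% | 14 | 14/271 = 5.2% |
| 20 | 7.0% | 8 | 8/265 = 3.0% |
| 25 | 8.8% | 3 | 3/260 = 1.2% |
| 28 | 9.8% | 0 | 0% |

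Equivalently, with error rate e in the remaining patients, a share s can be wholly missed when s + (1 − s)e < 0.10, so s < (0.10 − e)/(1 − e). That gives s below 8.2% at e = 2%, 5.3% at e = 5% and 2.2% at e = 8%.

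**4. When so small an endotype must exist.** The smallest of k endotypes holds at most floor(285/k) patients. This is 31 (10.9%) at k = 9, 28 (9.8%) at k = 10, 25 (8.8%) at k = 11 and 23 (8.1%) at k = 12. An endotype under 10% is therefore unavoidable at k = 10 to 12. At k = 2 to 9 it occurs only if sizes are sufficiently unequal.

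**5. How much of it is missed.** This was simulated under assumptions that are not the plan's: endotypes of 157, 108 and 20 patients, with 100 marker genes each for the second and third, shifted by 1.2 SD. A random forest was run with ten-fold cross-validation, and genes were added until the overall error fell below 10%.

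- Genes ordered by F ratio: stopping came at about 6 to 10 genes with error of about 8.8% to 9.6%. Sensitivity was 96% to 99% for the two large endotypes and about 0% (under 1% on average) for the third.
- Genes ordered one-versus-rest: sensitivity for the third endotype was 30% to 60% at 1.2 SD and 40% to 75% at 2.0 SD, in 5 runs each. A further set of runs gave 45% to 85%.

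The plan does not say how genes will be ordered, so both results are open under it.

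**6. Whether balanced error alone would repair the rule.** With one endotype wholly missed and the rest perfect, the mean of the per-endotype error rates is 1/k. That is 25% at k = 4 and 10% at k = 10, which both fail, but 9.1% at k = 11 and 8.3% at k = 12, which both pass. A limit on each endotype is needed.

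**The case against.** The strongest reply is that the fault needs a small endotype, and the documents do not predict one. Their precedents are two endotypes in pediatric sepsis (section 1.2) and four in adult sepsis from 306 subjects (section 6.5). In simulated correlated expression data, the smallest hierarchical cluster held about 36% to 43% at k = 2, 21% at k = 3 and 13% to 16% at k = 4. It reached 9% to 10% only at k = 6. The 50:50 split in section 6.4.2 is an assumption for the mortality power statement and does not settle the matter. This objection stands as a limit on likelihood. It does not change what the rule permits, since k may run to 12 with no size check.

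A second reply is that the word overall does not appear in the rule. That is true, but an unqualified misclassification rate is ordinarily errors over all patients, and nothing in the plan says otherwise.

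A third is that the consequence is small. At the assumed 16% mortality, 28 derivation patients would have about 0.16 × 28 = 4.5 deaths. A proportionate 19 of the 190 test patients would have about 3. Merging 20 patients into 157 makes them 20/177 = 11% of that group. The plan also says it is not powering for mortality. This stands too: the loss concerns which endotypes are recognised more than any mortality estimate.

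A reader might also infer that the rule could be met by genes carrying no information. With random 92:8 labels and 20 noise genes, error was indeed 8.1% with minority sensitivity of 0%. That does not represent this analysis, because the labels are clustered from the same expression data and informative genes therefore exist. With a real 92:8 cluster, the rule stopped at 2 genes with minority sensitivity of 35% to 65% at 1.2 SD and 78% to 91% at 2.0 SD.

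**Conclusion.** The concern holds as a possibility that the rule allows. In 285 patients, an endotype of 28 or fewer can be largely or wholly misclassified and the gene set still accepted, if all errors together total no more than 28. It rests on the ordinary reading of the error rate, on 475 evaluable subjects, and on at least one endotype falling under 10%. With few, balanced endotypes it does not arise. The extent of the loss, from nearly all of the small endotype to a minority of it, depends on the unstated gene ordering.

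The consequence that follows is that the final gene set may not identify a discovered endotype, and that test-set patients assigned by it would be merged into larger ones. Two stronger readings are not supported. A reader might infer that the rule is met whenever an endotype under 10% is missed; it is not, because the other errors count too. A reader might also infer that the endotype would vanish from the outcome analyses altogether. Derivation patients already carry cluster labels, and no section says that the gene set replaces those labels for the mortality or treatment-response analyses. This is a modest defect that is cheap to correct.

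**What to change.** In section 6.4.2, stop adding genes only when the overall cross-validated error is below 10% and every endotype also meets a pre-stated limit on its own error rate or sensitivity. The sponsor sets that value. Use folds stratified by endotype. Report any endotype that never meets the limit as not classifiable. Apply to the transcriptomic clustering the check on smallest-class size that the latent class analysis already has. Do not rely on balanced error alone.

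The cost is a change of wording and an extra summary from the same cross-validation, with no new patients or assays. The downside is a larger gene set, or a small cluster declared not classifiable. As an illustration, in the 157/108/20 example with F-ratio ordering, a related criterion was tried: balanced error below 10%, an 80% sensitivity floor and a class-weighted forest. It was met in 7 of 8 runs, usually at 120 genes, with 80% to 90% sensitivity for the third endotype. In the eighth run that endotype reached only 70% at 200 genes, so the failure was visible.

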6.4 Statistical Methods

6.4.1 Baseline Data

Baseline and demographic characteristics will be summarized by standard descriptive summaries (e.g., means and standard deviations or medians with interquartile ranges for continuous variables and proportions for categorical variables). Comparisons between survivors and non-survivors, and later between different endotypes, will be tested using unpaired t-test or Wilcoxon rank sum test for continuous variables. The analogues of these tests for > 2 groups (ANOVA and Kruskal-Wallis) will be used if > 2 endotypes are identified. Fisher's exact or chi-squared test will be used for categorical variables.

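### Aim 3 latent class analysis: indicators are standardized but not transformed, so if plasma markers are right-skewed the classes can reflect skewness rather than biology

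*Combined protocol and SAP*

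**What the plan says.** All of this is in section 6.4.2, protein biomarker part of Aim 3, unless stated otherwise.

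- Indicators: "We will use all measured plasma biomarkers and select clinical variables recorded within 24 hours of ARDS onset". The clinical variables named are age, vasopressor-inotrope score, PELOD 2, bicarbonate and OI at onset. The number of biomarkers is not given.
- Pre-processing: "As scales of variables vary considerably, continuous variables will be standardized to mean" 0 and standard deviation 1. The reason given concerns units and not distribution shape.
- Candidates: "We will consider models between 2 and 5 subclasses". A one-class model is not listed.
- Selection: "the Bayesian Information Criteria, the Vuong-Lo-Mendell-Rubin likelihood ratio test, and size of the smallest class". No minimum class size is stated.
- Estimation: "Model estimation will be based on full-information maximum likelihood methods". The within-class distribution and the variance and covariance structure are not stated.

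Section 6.4.1 allows for non-normal data through "means and standard deviations or medians with interquartile ranges for continuous variables" and rank tests, but only for descriptive tables and group comparisons. Section 6.4.2 mentions normalizing for gene expression only. Section 6.1 makes the generation of new endotypes the endpoint of Aim 3.

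**The concern.** The usual maximum-likelihood latent class model for continuous indicators takes each indicator as normal within class. Concentrations cannot be negative, so right skew is plausible. A normal mixture can fit the long tail of one homogeneous skewed population by adding classes, and BIC may reward the better fit.

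The classes are themselves the Aim 3 endpoint. Sections 2.2 and 6.2 then relate them to mortality, ventilation outcomes and treatment response. An error in class number or membership carries into each of those analyses. It also matters if real endotypes exist, because skewness can blur or split them.

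**Working it through.** The plan gives no figure for marker distributions or class-recovery error, so there is nothing of its own to reproduce.

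**Step 1: what standardizing does.** For z = (y − m)/s, skewness is E[(y − m)³]/s³, the same as for y. If the model estimates a variance for each indicator, z-scoring also shifts the log-likelihood by the same constant for every number of classes. It therefore cannot change which solution BIC prefers.

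**Step 2: inputs.**
- From the documents: 500 evaluable subjects for the plasma aims (section 3.3.2) and a 60:40 split, so 0.6 × 500 = 300 for derivation and 200 for test.
- Assumed: 8 lognormal markers, log-scale SD 0.25 to 1.5, log-scale correlation 0 or 0.3, a 5% class-size floor, and normal locally independent indicators within class.
- Skewness of a lognormal with log-scale SD σ is (exp(σ²) + 2)·√(exp(σ²) − 1). For σ = 0.5 this is (1.284 + 2) × √0.284 = 1.75.
- Fit: EM with multiple starts, K = 1 to 5, chosen by BIC, 20 data sets per cell.

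**Step 3: no true classes, independent markers.** Share of data sets in which BIC chose more than one class:

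| log-SD | skewness | z-score only, equal class variances | same, with 5% floor | z-score only, free class variances | logged, then z-scored |
|---|---|---|---|---|---|
| 0.25 | 0.8 | 30% | 15% | 55% | 0% |
| 0.5 | 1.8 | 100% | 80% | 100% | 0% |
| 0.75 | 3.3 | 100% | 70% | 100% | 0% |
| 1.0 | 6.2 | 100% | 30% | 100% | 0% |
| 1.5 | 33.5 | 100% | 20% | 100% | 0% |

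With free variances the 5% floor changed nothing. A separate run with K = 1 to 3, equal variances and 30 data sets gave 20% at log-SD 0.25. With 20 data sets the percentages are approximate: 20 out of 20 has an exact lower 95% limit of 0.025^(1/20) = 0.83.

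**Step 4: two true classes** (35:65, one SD apart on the log scale; log-SD 0.5, 1.0 and 1.5). With z-scores only, BIC chose two classes in 0% of data sets. Agreement of the two-class fit with truth (adjusted Rand index) fell from 0.49 to 0.04 with equal variances, and from 0.48 to 0.37 with free variances, as skew rose. After logging, BIC chose two classes in 100%, with agreement of about 0.70.

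**Step 5: a mix of indicators.** With 8 lognormal and 3 normal indicators (equal variances, 12 data sets per cell) the direction was the same. With no true classes, extra classes appeared in 100% when z-scored only and in 0% after logging. With two true classes, BIC chose about five classes against exactly two, and two-class agreement was 0.60 against 0.90 at log-SD 1.0.

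**Step 6: does the test set protect?** In independent samples of 200 with no true classes, z-scored markers again gave at least two classes in 100% of data sets at log-SD 0.5 and 1.0. Test-set markers share the skew, so false classes can appear to replicate.

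**Step 7: limits of logging.** With log-scale correlation 0.3 and no true classes, logged markers still gave more than one class in 100% of data sets (mean K 2.9 with equal variances, 2.15 with free). With independent logged markers but only K = 2 to 5 allowed, BIC returned two classes in every one of 15 data sets per cell, because one class was not an option.

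**The case against.** The strongest reply is that the plan is silent on transformation and does not refuse it. An analyst could log the markers and still comply. The documents report no marker distribution and no within-class model, so both the skew and the normality are assumed here. Some named indicators (age, bicarbonate, PELOD 2) need not be skewed. At mild skew an extra class is far from certain.

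The plan also has safeguards that BIC alone does not represent. Class size is a stated criterion, and a small tail class is what it would catch: with equal variances a 5% floor cuts false classes from 100% to 20% at log-SD 1.5. The Vuong-Lo-Mendell-Rubin test at two classes sets one class against two, and it was not simulated. Finally, when markers correlate, false classes persist after logging, so skewness is not the only cause.

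Most of this stands, and it limits the claim. A reader might infer that the plan has decided to analyse raw values and that its classes will be spurious. The documents support neither inference. A reader might also infer that any link between such a class and mortality would only restate that extreme values are harmful. No outcome was simulated, so that is untested.

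The reply does not remove the point. Followed literally, the only stated step puts untransformed markers into the model. The size criterion has no threshold, and the floor did not help with free variances. Random starts address local maxima, not misspecification. No rule says what happens if the likelihood ratio test favours one class.

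**Conclusion.** The concern holds in conditional form. As written, section 6.4.2 leaves skewness in the indicators. If plasma markers are moderately or strongly right-skewed and the model is normal within class, class number and membership can reflect skewness.

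The size of the effect depends on the skew. With independent markers it is 100% against 0% of homogeneous data sets at log-SD 0.5 or more, and about 20% to 55% at log-SD 0.25, all judged by BIC with one class allowed. The direction is well supported. The percentages rest on the assumed marker number, skew, correlation and model, on few replicates, and on only part of the plan's selection rule. Logging is a clear improvement but not a full remedy when markers are correlated.

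**What to change.** Amend section 6.4.2 before any latent class model is fitted, while the analysts are still blinded to outcome:

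1. Log-transform right-skewed biomarkers and other skewed continuous indicators, then standardize with derivation-set means and SDs, applying the same values to the test set.
2. Handle variables with many zeros, such as the vasopressor-inotrope score, separately, for example as a categorical or two-part indicator. Taking log(x + 1) leaves every zero at zero and does not normalize the cluster.
3. List one class among the candidates (K = 1 to 5), so that finding no classes is a possible result.
4. Also fit a model that allows within-class covariance among the markers, and report whether the class solution holds.
5. State the within-class distribution, whether class variances are equal or free, and the minimum class size, since the simulated results turn on these.

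The cost is a few sentences in the plan and a few more model fits, with no new data. The downside is that fewer classes, or none, may be found.

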6 STATISTICAL CONSIDERATIONS

6.1 Primary Endpoint

The primary endpoint of Aim 1 is successful performance of the PARDSEVERE risk stratification tool to discriminate 28-day mortality in pediatric ARDS. The primary endpoint of Aim 2 is application of a known 100-gene classifier to test whether transcriptomic endotypes exist in pediatric ARDS. The endpoint of Aim 3 is generation of novel proteomic and transcriptomic endotypes.

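### The endotype searches list no one-class candidate, and the plan has no rule for concluding that no distinct endotypes were shown

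*Combined protocol and SAP*

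**What the plan says.** **The question.** Section 6.1 gives the Aim 2 endpoint as applying a known 100-gene classifier "to test whether transcriptomic endotypes exist in pediatric ARDS". Section 2 says the work will establish that biomarker-defined endotypes are present and clinically relevant. Section 1.2 calls it unknown whether clinically relevant endotypes exist in pediatric ARDS, and makes that the key goal of Aims 2 and 3.

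**The searches (section 6.4.2).** For the protein part of Aim 3: "We will consider models between 2 and 5 subclasses, as has been done for adult ARDS". The choice among models rests on three things: "criteria for model selection will be based on the Bayesian Information Criteria, the Vuong-Lo-Mendell-Rubin likelihood ratio test, and size of the smallest class". For the transcriptomic part: "We will then perform unsupervised agglomerative hierarchical clustering on the top 5000 probesets, with clusters allowed" to run from k = 2 to 12. To choose k, "we will combine cumulative distribution functions and cophenetic distance correlation analysis to assess clustering stability". A random forest is then trained on the cluster labels: "We will decide on the final number of endotype-defining genes when the process yields a cross-validation misclassification error rate of" less than 10%.

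**The split.** Both parts divide the cohort 60:40 into derivation and test sets. Neither says what the test set must show. Genes are ranked by median absolute deviation over all patient samples, which on its face includes the test set.

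**The comparisons (section 6.4.1).** "Comparisons between survivors and non-survivors, and later between different endotypes, will be tested using unpaired t-test or Wilcoxon rank sum test" for continuous variables. ANOVA and Kruskal-Wallis "will be used if > 2 endotypes are identified". The one-class case is not described.

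**The concern.** A study that asks whether endotypes exist needs a result that would count as no. Here the candidate lists start at two. The stability measures rank the values of k that were tried, but they are not compared with what one unstructured population would give. The one listed test that has one class as its null carries no significance level, no priority over the other criteria and no consequence. Aim 1, by contrast, has explicit pass marks for sensitivity and specificity.

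If patients lie along one continuous axis, such as severity, the procedure still cuts that axis into groups. Two later outputs could then be mistaken for confirmation: a low classifier error on labels made from the same expression data, and very small p-values for the variables that formed the groups. The stake is future trials enriched on classes that are only segments of a gradient.

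**Working it through.** The plan gives no error rate or power for endotype discovery, so there is no figure of its own to reproduce. The check reads the rules as written and applies them to simulated data that contain no classes.

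**Inputs from the documents.** Latent class candidates 2-5; clustering k = 2-12; ten-fold cross-validation with a 10% error limit; 500 plasma and 475 RNA subjects; 16% mortality. The derivation sets are 0.60 × 500 = 300 and 0.60 × 475 = 285; the test sets are 200 and 190.

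**Assumptions.** The documents do not give the number of latent class variables or any correlation structure or skewness, so those used here are assumed. So is the use of 1,000 genes, where the plan clusters the top 5,000 probesets.

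**1. Choosing the number of latent classes.** A latent profile model with class-specific means and common variances was fitted to n = 300 and p = 15 standardized variables, 40 datasets per scenario.

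BIC(k) = −2 log L(k) + q(k) ln n, with q(k) = kp + p + (k − 1).

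q(1) = 15 + 15 + 0 = 30 and q(2) = 30 + 15 + 1 = 46. For two classes to beat one, 2[log L(2) − log L(1)] must exceed (46 − 30) × ln 300 = 16 × 5.704 = 91.3. When one class is not a candidate, BIC never applies this hurdle.

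| One-class data | BIC over 2-5 | BIC over 1-5 |
|---|---|---|
| Independent normal | 2 classes, 40/40 | 1 class, 40/40 |
| One continuous factor (pairwise correlation 0.6² = 0.36) | 3 classes in 13, 4 in 27 | the same |
| Skewed (log-normal, log SD 0.7) | 4 classes in 4, 5 in 36 | the same |

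A result of 40/40 has an exact lower 95% limit of 0.025^(1/40) = 0.91. Row 1 shows the effect of leaving one class out. Rows 2 and 3 show that adding it does not by itself protect against correlation or skewness. The reason is that the one-class null in such a model assumes independent variables of the fitted shape, so departures from it need not mean that classes exist.

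**2. Classifier error on cluster labels.** Ward clustering was cut at k = 2 with n = 285, followed by a random forest with ten-fold cross-validation, 6 datasets per scenario. Genes were ranked once on the whole derivation set.

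| Data without classes | Mean error, 25/100/400 genes | Datasets under 10% | Clustered genes with p < 0.05 |
|---|---|---|---|
| One continuous axis | 4.4/3.6/3.3% | 6/6 | 80% |
| One strong axis | 1.9/1.7/1.6% | 6/6 | 90% |
| Five axes | 12.6/12.2/11.3% | 2/6 | 71% |
| No structure | 22.7/23.2/28.4% | 0/6 | 11% |

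Six datasets is few: 6/6 has a lower 95% limit of 0.025^(1/6) = 0.54. The table shows that the 10% limit can be met without classes, and that it is not always met.

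**3. Tests between classes, from the runs in step 1.** Of the variables that formed the classes, 54% (independent), 100% (correlated) and 33% (skewed) had p < 0.05, against a nominal 5%. An unrelated outcome with 16% frequency gave p < 0.05 in 0-3% of datasets, so it was not inflated.

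**The case against.** **A reader might infer that the plan can never conclude against endotypes, or that two classes are never tested against one.** The documents do not support that. The Vuong-Lo-Mendell-Rubin test compares k with k − 1 classes, so at k = 2 its null is one class. What is missing is a cut-off and an action. The test also covers only the latent class part; nothing equivalent exists for the clustering.

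**A reader might infer that the 10% error limit is an automatic pass that stands in for proof.** Section 6.4.2 uses it to fix the number of genes and does not offer it as evidence of classes, and it failed in the unstructured data above. What stands is that meeting it must not later be read as evidence.

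**A reader might infer that every between-endotype test is circular.** Section 6.4.1 concerns baseline description, and no section uses its p-values to establish endotypes. The overlap is limited to variables that formed the classes: for the latent class analysis, the biomarkers, age, vasopressor-inotrope score, PELOD 2, bicarbonate and OI. Clinical variables are not inputs to the transcriptomic clusters. Mortality and ventilator-free days are inputs to neither.

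**A reader might infer from the order of section 6.4.1 that outcome could influence the classes.** Sections 6.3 and 6.4.2 blind class formation to outcome.

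**The aims are partly exploratory.** Section 6.1 ties the existence question to a fixed published classifier, which is not a search over k, and defines the Aim 3 endpoint as generating endotypes. This has some force. However, section 6.4.2 places the clustering under Aim 2, and section 2 promises to establish presence. A held-out test set exists, which is to the plan's credit, but it has no stated criterion.

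**Conclusion.** The concern holds in this form: the data-driven searches omit one class, and no stated result of the two-versus-one test, the stability analysis or the test set would lead to the conclusion that no distinct endotypes were shown. A continuous gradient can therefore be reported as two or more endotypes.

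That the candidate lists return at least two classes follows from the text and needs no simulation. The simulations show what this does in homogeneous data. With independent variables, the planned range gave two classes every time where a range including one gave one class every time. With correlated or skewed variables, 3-5 classes appeared under either range. These counts rest on the assumed number of variables, correlation and skewness. The classifier results rest on six datasets per scenario and 1,000 genes.

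The p-values in section 6.4.1 are invalid as evidence only for class-forming variables. The planned associations with mortality and ventilator-free days are not affected.

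**What to change.** 1. Fit the one-class latent class model and report it with the others.
2. State the negative rule. The conclusion is that no distinct endotypes were shown if the two-versus-one test is non-significant at a stated level, or if the BIC gain or cluster stability statistic does not exceed a pre-stated reference. Take that reference from data simulated from a single population matched to the derivation set's covariance and marginal shape. Step 1 without this reference is not enough.
3. Do gene ranking, clustering and gene-number choice in the derivation set only, replacing the ranking over all patient samples.
4. Use the 40% test set to check replication against an agreement criterion fixed in advance. The percentile of the null distribution (for example the 95th) and the agreement index (for example adjusted Rand) are choices among several valid options; what matters is that they are stated beforehand.
5. For class-defining variables, report standardized differences without p-values.
6. Say that the 10% error limit sets the number of genes and is not evidence that classes exist.

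The cost is wording in section 6.4 and extra computing; no further subjects or samples are needed. The downside is that the result may be fewer endotypes, or none.
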